Official Title: Esophageal Food Impaction (ONEFIT)

NCT#: NCT03305848

Study Protocol and Statistical Analysis Plan

Document Date: July 26, 2017

Participant Contact Project Narrative

1. Summary

A piece of food stuck in the esophagus (the tube connecting the mouth to the stomach) is a relatively common occurrence, estimated at a rate of 13 episodes per 100,000 people per year, mostly men, and usually attributed to swallowed meat. The current standard of care for patients presenting to an Emergency Department with this problem includes a trial of medication, usually glucagon but sometimes a carbonated beverage, an injection of nitroglycerin, or benzodiazepines. The medical interventions mentioned above have not been shown to be significantly effective and have unwanted side effects; glucagon is known to cause nausea and vomiting and benzodiazepines can cause sedation and depressed breathing. If the medication fails to relieve the problem, the patient may require a procedure called endoscopy, where a video scope and retrieval tool are inserted into the esophagus to remove the piece of food. There is significant risk associated with endoscopy, including the risks of anesthesia as well as with the physical procedure itself. Endoscopy also results in a prolonged hospital stay due to the time required for the procedure, as well as from anesthesia recovery. The ideal treatment would be a safe, inexpensive, quickly effective medication without significant side effects that could be administered without sedation or extensive monitoring. Oral nitroglycerin solution might just be that intervention.

2. Study aims

Obtain exploratory data on the safety and efficacy of oral nitroglycerin solution for the treatment of esophageal food impaction in a cohort of patients presenting to the ED with presumed esophageal food impaction.

Aim 1: Efficacy. We will determine the success rate of oral nitroglycerin solution in relieving the food impaction by assessing the resolution of symptoms and the ability of the patient to swallow.

Aim 2: Safety. We will calculate the frequency of adverse events from this medical intervention. We are mainly concerned with hypotension, lightheadedness, headache, allergic reaction, dyspnea, vomiting, and pain.

3. Background, Rationale, Significance

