1. Study subjects who meet all of the inclusion criteria and none of the exclusion criteria will be approached for consent by study staff prior to enrollment. If an eligible patient is not being cared for by the PI or a Co-I, study staff must approach the patient's provider to determine if it is appropriate to proceed with the consent process. If additional testing needs to be done to see whether a patient meets criteria for entry into the study, the PI, a Co-I, or staff will need to consent the patient first. If the preparation activity confirms a patient is a possible subject, PI/research staff approaches the patient to begin the consent process.

iv. Data sources

1. Study subjects will be interviewed prior to treatment and again after treatment. Medical records from the visit will be collected.
2. Please see attached chart titled "Data Collection Form" describing the variable name, data source, purpose, and measurement scale in the initial application submission

v. Process steps for data acquisition

1. The study subject's demographical, medical, and surgical history, and symptom data will be initially collected from medical record and interview by investigators and/or research assistants during the Emergency Department visit. First at enrollment, then after each administration of study medication. Data will be collected by study investigators and/or research assistants. Data collected includes:
 - Medical record number (MRN), Age, Gender, Visit date, Allergies, Blood pressure, Presenting complaint / HPI, Symptoms throughout the ED visit, medical history, surgical history, time and dose of medications administered
2. The patient's ED provider will be asked for appropriateness for inclusion in the study (yes to any answer will count as an exclusion). They will be asked:
 - a. Is symptoms onset more than 12 hours ago?
 - b. Is there concern for airway obstruction?
 - c. Is there concern for esophageal perforation?
 - d. Is there concern for coronary ischemia?
 - e. Are there any other concerns about including this patient in the study?
3. After discharge of the patient (either from the ED or after admission), their medical record will be accessed for data abstraction by investigators and/or research assistants. The following data will be collected:
 - a. Disposition from the ED
 - b. Length of stay
 - c. Procedures performed during the visit
 - d. Medications given during the visit
 - e. Condition at discharge

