4. A single follow-up phone call will be made by investigators and/or research assistants between 4-7 days after discharge to obtain:
 - a. Symptoms at discharge
 - b. Symptoms currently
 - c. Any other treatment required since hospital discharge
 - d. Satisfaction survey

d. *Intervention, treatments*

- i. Up to 3 administrations of 0.4mg sublingual nitroglycerin tablets, dissolved in 10mL tap water, given orally in a single swallow. Each administration is separated by at least 5 minutes, and only if systolic blood pressure > 100 mmHg. The patients then have to pass a swallow test before discharge. The passing of the swallow test will indicate a treatment success. Treatment failure is

defined as lack of symptom resolution 10 minutes after the last dose of nitroglycerin OR inability to tolerate administration OR intolerable side effects.

e. Outcomes/endpoint and other variable definitions, and instruments used

- i. Primary Endpoint is the patient is able to swallow without difficulty within 10 minutes after nitroglycerin administration.
- ii. Secondary endpoint is adverse events during the hospital stay.

f. Statistical analysis plan

- i. Descriptive statistics will be used to summarize the study sample and to evaluate efficacy of the study intervention and frequency of side effects. Specifically, we will first calculate summary statistics (mean \pm standard deviation, frequency counts and percentages) for relevant patient factors (demographics, etc.) at the time of presentation to the ED. We will then calculate the proportion of study patients who achieve resolution of food impaction, with a corresponding 95% confidence interval. Similarly, we will also report frequencies of adverse events, overall and by type of adverse event, along with appropriate measures of variance (including headache frequency and change in blood pressure). Finally we will report outcome statistics (frequency counts and percentages) for repeat symptoms subsequent to the hospital visit (from follow up phone call). Symptom data from follow-up phone call will be used, non-statistically, to identify possible delayed complications of oral nitroglycerin use.

g. Power analysis or statement of precision

- i. No formal hypothesis testing will be pursued, thus we have not conducted a power analysis.. Given the proposed sample size ($n=20$), and projecting 90% success in resolving food impaction (18/20), we anticipate a 95% confidence interval of (68.3%, 98.8%).

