- b. Because of the protective safeguards in place to protect patient privacy, there is a very low risk to a patient's loss of privacy, risk to reputation or other social risks. The only data that will be accessed from the patient's medical record will be data that is related to the specific admission and meet the defined data abstraction elements.
- c. All eligibility screening, enrollment, randomization, and data entry will take place in the CCRC. The CCRC is a secure, locked department with limited access for security purposes. All patient charts and paper case report forms, including signed consent forms, will be stored in locked file cabinets in the CCRC. A master database linking the subject number and patient name will be maintained on a password-protected server only available to research staff. This is a secure, electronic system that is currently used at Regions Hospital and is approved by IS&T Security. All study data will be coded and de-identified.

8. Timeline

- a. This study is proposed to be completed within 1 year.
 - i. April 2017: IRB Submission
 - ii. May 2017: IRB Approval
 - iii. August 2017: Educate providers and CCRC research staff on enrollment criteria
 - iv. August 2017- August 2018 Enroll patients and collect data
 - v. July 2018 Analyze data and write abstract/manuscript for submission

9. Dissemination/Sharing Results/Integration and Impact

- a. We will prepare the results of the study for publication, with potentially significant impact on routine management of esophageal food impaction by Emergency medical providers.

10. References

- a. Robbins M, Shortsleeve M. Treatment of Acute Esophageal Food Impaction with Glucagon, an Effervescent Agen, and Water. *Am J Roentgenology*. 162:325-28. 1994.
- b. Management of Ingested Foreign Bodies and Food Impactions. *Gastrointestinal Endocscopy*. 73(6):1085-91. 2011.
- c. Ko HH, Enns R. Review of Food Bolus Management. *Can J Gastroenterol*. 22(10):805-8. 2008.
- d. Dellon ES, et al. ACG Clinical Guideline: Evidenced Based Approach to the Diagnosis and Management of Esophageal Eosinophilia and Eosinophilic Esophagitis (EoE). *Am J Gastroenterol*. 108:679-92. 2013.
- e. Weant KA, Weant MP. Safety and Efficacy of Glucagon for the Relief of Acute Esophageal Food Impaction. *Am J Health-Sys Pharm*. 69:573-77. 2012.

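### The adverse event endpoint covers the hospital stay, but the plan as supplied lists no direct adverse event collection after the ED, so events in admitted patients may be under-counted

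*Combined protocol and SAP*

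**What the plan says.** The window is set in section 4.e.ii: "Secondary endpoint is adverse events during the hospital stay". Aim 2 in section 2 names the events that matter: "We are mainly concerned with hypotension, lightheadedness, headache, allergic reaction, dyspnea, vomiting, and pain". Section 4.f will report their frequencies, overall and by type.

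Collection is described in section 4.c.v, in three steps:

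- **Prospective (4.c.v.1).** Data are initially "collected from medical record and interview by investigators and/or research assistants during the Emergency Department visit". The timing is "First at enrollment, then after each administration of study medication". The items include "Blood pressure, Presenting complaint / HPI, Symptoms throughout the ED visit".
- **Chart abstraction (4.c.v.3).** "After discharge of the patient (either from the ED or after admission), their medical record will be accessed for data abstraction". Five items are listed: ED disposition, length of stay, procedures, medications and condition at discharge.
- **Phone call at 4-7 days (4.c.v.4).** It asks about symptoms at discharge, current symptoms, further treatment and satisfaction.

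Section 7.b adds that the only data accessed from the medical record "will be data that is related to the specific admission and meet the defined data abstraction elements". Section 4.c.iv says that records of the visit will be collected, and refers to a Data Collection Form that is not among the supplied documents.

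**The concern.** The endpoint window is wider than the window over which the supplied text collects events directly. For a patient who goes from the ED to endoscopy or a ward, no listed item directly records hypotension, vomiting, dyspnea, pain or the other Aim 2 events after that point.

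Safety is one of only two aims. The protocol describes endoscopy as the backup when medication fails (section 3) and counts avoiding admission and endoscopy among the benefits of treatment (6.b). The patients whose later hours are least well covered are therefore likely to include treatment failures. Failure is defined in 4.d to include intolerable side effects and inability to tolerate administration, so some of these patients may have had tolerability problems. If the adverse event table divides by all 20 patients, time that was not observed would in practice look like time without events.

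**Working it through.** **1. Endpoint against sources.** The question for each source is whether it records an Aim 2 event that occurs after the ED and before discharge.

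| Source | Reaches the inpatient stay? | Records Aim 2 events directly? |
|---|---|---|
| 4.c.v.1 symptoms | No, limited to the ED visit | Yes, within the ED |
| 4.c.v.1 blood pressure | No window of its own; the step is tied to the ED visit and to doses | Yes (hypotension) |
| 4.c.v.3 abstraction, five items | Yes | No; procedures, medications and condition at discharge are indirect signs |
| 4.c.v.4 phone call | Asks about discharge and the day of the call | Not about events during the stay |
| 4.c.iv visit records | Possibly | Unclear; 7.b limits access to defined elements |
| Data Collection Form | Unknown | Unknown |

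Section 4.f uses the call for counts of repeat symptoms and, without statistics, for delayed complications. It does not use the call for the adverse event frequency. No section says how a patient with incomplete ascertainment enters that frequency.

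**2. The plan's own figure.** The only computed figure is the interval in 4.g for 18/20 successes, 68.3% to 98.8%. The exact (Clopper-Pearson) limits for x events in n patients are:

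- lower = Beta quantile(0.025; x, n-x+1)
- upper = Beta quantile(0.975; x+1, n-x)

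With x = 18 and n = 20 these give 68.30% and 98.77%, so the plan's interval is reproduced. The same method is used below.

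**3. What one missed event does (n = 20, section 4.b.ii).**

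- 1/20 = 5%, exact 95% CI 0.1% to 24.9%
- 0/20 = 0%, upper limit 1 - 0.025^(1/20) = 16.8%

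**4. How likely a missed event is (illustration only).** The documents give neither an admission rate nor an event rate after the ED. Let a be the share admitted and q the chance that an admitted patient has an Aim 2 event after the ED. If none of these events were captured, the expected number missed is 20aq and the chance of at least one is 1 - (1 - aq)^20.

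| a | q | 20aq | Chance of at least one |
|---|---|---|---|
| 10% | 5% | 0.1 | 10% |
| 30% | 10% | 0.6 | 46% |
| 50% | 20% | 2.0 | 88% |

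Indirect capture would lower these figures.

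**5. The denominator.** If only patients observed for the whole stay were counted, a zero would carry a wider interval than 0/20 with its upper limit of 16.8%. With 30% admitted, 14 remain: 0/14, upper limit 1 - 0.025^(1/14) = 23.2%. With 50% admitted, 10 remain: 0/10, upper limit 1 - 0.025^(1/10) = 30.8%.

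**The case against.** The strongest reply is that the variables are defined in the Data Collection Form, which cannot be checked here. The form may contain adverse event and vital-sign fields. Section 7.b does not say that the defined elements are only the five in 4.c.v.3. Blood pressure and symptoms in 4.c.v.1 also have the medical record as a source, and blood pressure carries no window of its own. This stands, and it makes the point conditional on the form.

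A second reply is that the period most relevant to the drug is covered. Data are taken after each dose, and section 6.a describes the half-life as very short. Events later in the stay may come from endoscopy or anesthesia, whose risks sections 1 and 3 acknowledge. This also stands. It is a reason to narrow the endpoint or to separate procedural events, but not to state a window that is not observed.

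A reader might infer that symptoms are collected only in the ED, or that nothing is collected afterward. The documents do not support either reading. The phone call asks about symptoms, and the abstraction could reveal treated or serious events through procedures, medications and condition at discharge. Capture after the ED is incomplete, not absent.

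**Conclusion.** The point holds in conditional form. The stated endpoint runs to the end of the hospital stay, and the supplied text does not define how Aim 2 events after the ED are ascertained in admitted patients. Unless the Data Collection Form fills the gap, those events would be incompletely captured and a frequency over all 20 patients would probably be too low. In a cohort of this size a single missed event is enough to change a reported 1/20 to 0/20.

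Two stronger conclusions are tempting but not supported:

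- **That events not ascertained will be counted as none.** The plan has no such rule. It is the likely result if all 20 patients form the denominator.
- **That 10-30% of the cohort lacks safety data.** This takes the failures at the projected success rate, 20 x (1 - 0.90) = 2, and at the lower confidence limit, 20 x (1 - 0.683) = 6.3, and assumes that failures are exactly the patients who leave the ED for further care. The documents give no admission rate and do not state that link.

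**What to change.** First check the Data Collection Form. If the fields are absent, add two items to 4.c.v.3 and to the form; if they are present, bring 4.c.v.3 into line with it:

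- any Aim 2 adverse event documented from first dose to discharge, with onset time;
- recorded blood pressures with times, over the same period.

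Listing them makes them defined elements under 7.b. Report events before and after the start of any endoscopy or sedation separately, so that procedural events are not mixed with those that follow nitroglycerin. This also needs the start time of the procedure or sedation.

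Alternatively, restate 4.e.ii as adverse events during the ED visit, which is the window in which symptoms are collected.

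Under either option, state in 4.f the denominator for adverse event frequencies and how patients with incomplete ascertainment are handled.

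The cost of the first option is a few more minutes per chart, on 20 charts that staff already open after discharge. The overall event rate may also be higher because it includes events from endoscopy or sedation, which is why the split is needed. The second option needs no extra collection but gives up any claim about safety after the ED.

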Esophageal food impaction is a relatively common illness, estimated to occur at a rate of 13 episodes per 100,000 people per year, mostly men, and usually attributed to swallowed meat bolus. Current standard of care for patients presenting to an Emergency Department with presumed esophageal food impaction includes trial of medical therapy, usually glucagon but sometimes effervescent liquid, sublingual or intravenous nitroglycerin, or benzodiazepines, with a backup of endoscopy for definitive mechanical removal of the food bolus. Glucagon has significant uncomfortable side effects, chiefly nausea and vomiting. The medical interventions mentioned above have not been shown to have significant efficacy; endoscopy is frequently performed after failure of medical management. There is significant risk associated with endoscopy, including the risks of anesthesia as well as with the physical procedure itself. Endoscopy also results in a prolonged hospital stay due to the time required for the procedure, as well as from anesthesia recovery. The ideal treatment would be a safe, inexpensive, quickly effective medical intervention without significant side effects that could be administered without sedation or extensive monitoring. Oral nitroglycerin solution might just be that intervention.

No published trials or case reports using oral nitroglycerin solution for esophageal food impaction were found. Two recent unpublished cases using oral nitroglycerin solution were remarkably and rapidly effective (within 2 minutes) in relieving esophageal food impaction symptoms. The currently proposed study would provide preliminary data which may motivate a larger controlled study.

4. Approach

a. Study design

Prospective, unblinded, single-arm cohort of patients presenting to the Emergency Department with presentation consistent with esophageal food impaction.

b. Population

i. Inclusion/Exclusion Criteria [See Human Subjects items to be moved here]

1. Inclusion Criteria:

- a. Over the age of 18 years
- b. Presentation consistent with esophageal food impaction
- c. Ability to swallow a small volume of liquid.

2. Exclusion Criteria:

- a. Intractable vomiting
- b. Hemodynamic instability or SBP <100 mmHg
- c. Concern for or evidence of significant airway compromise
- d. Concern for or evidence of esophageal perforation,
- e. Concern for or evidence of coronary ischemia
- f. Presentation > 12 hours since onset.

ii. Sample size

1. Convenience sample of 20 patients.

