h. Strengths and limitations

- i. Strengths
 1. New, promising medical intervention for esophageal food impaction with a strong theoretical likelihood of success.
- ii. Weaknesses
 1. Being a pilot study, further research will need to be undertaken to fully assess the safety and efficacy of the proposed intervention. We will not enroll a comparison group, statistical precision will be limited due to small sample size, and all results will be descriptive (no control for covariates).

5. Setting/Environment/Organizational feasibility

- a. This study is easily achievable, as the study cohort regularly presents to the Emergency Department, the study medication is inexpensive, universally available, and very easily administered.
- b. Research assistants are available 24/7/365 to help with enrollment and data collection.

6. Risks and Benefits

- a. The risks to study subjects are minimal. As with any medication, there is a risk of allergic reaction. Nitroglycerin causes vasodilation and has been associated with modest reduction in blood pressure, however this medication has been safely used for many years. The theoretical systemic absorption of oral nitroglycerin solution is slower than sublingual, and since its half-life is very short, systemic effects may very well be less prominent than with sublingual or intravenous administration.
- b. The benefits to study subjects include potentially rapid reversal of symptoms and food impaction with minimal delay or side effects, avoidance of admission and endoscopy, and avoidance of use of glucagon.

7. Data Confidentiality and Privacy

- a. This study is being conducted in accordance with the ethical principles that are consistent with the ICH and Good Clinical Practice. Once a patient is identified, they are assigned a unique identification number that is assigned to the patient for the duration of the study. The master database linking the patient MRN with the unique identification number is stored on a password-protected, secure share drive housed in the Critical Care Research Center. The CCRC is a locked office with limited accessibility. All

CCRC research staff have EPIC access via a unique user name and password that is monitored by IS&T Security. All research staff are fully trained on the elements of patient privacy, HIPAA and confidentiality.

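### Adverse events are counted over a hospital stay whose length tends to depend on treatment success, and delayed events found at the follow-up call stay outside the frequency

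*Combined protocol and SAP*

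**What the plan says.** Aim 2 (Section 2) promises a safety frequency: "We will calculate the frequency of adverse events from this medical intervention". It names hypotension, lightheadedness, headache, allergic reaction, dyspnea, vomiting and pain. Section 4.e.ii then sets the window: "Secondary endpoint is adverse events during the hospital stay".

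Three other places bear on how long that window is:

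- Section 4.d: "The patients then have to pass a swallow test before discharge. The passing of the swallow test will indicate a treatment success". No minimum observation time after the last dose is set for the safety endpoint.
- Section 3: "endoscopy is frequently performed after failure of medical management", and "Endoscopy also results in a prolonged hospital stay due to the time required for the procedure, as well as from anesthesia recovery".
- Section 6.b lists among the benefits "avoidance of admission and endoscopy, and avoidance of use of glucagon".

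Section 4.f reports adverse event frequencies overall and by type. It does not split them by treatment outcome or allow for observation time. Repeat symptoms from the call 4 to 7 days after discharge are tabulated as an outcome of their own. For complications the rule is different: "Symptom data from follow-up phone call will be used, non-statistically, to identify possible delayed complications of oral nitroglycerin use".

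**The concern.** The window for the secondary endpoint is each patient's length of stay, and length of stay is tied to the primary outcome. Treatment failures who need endoscopy stay longer, and successes are expected to avoid it. A single pooled frequency then mixes shorter windows with longer ones, in proportions set by the success rate.

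The call does not even this out. It is timed from discharge, not from dosing. Its listed items (4.c.v) are symptoms at discharge, current symptoms, further treatment and satisfaction. None of them asks what happened in between, so an untreated headache that began after discharge and had gone by day 4 could go unrecorded. A complication that the call does find stays outside the frequency.

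Safety is one of only two aims, and Section 3 presents the study as a possible basis for a larger controlled trial. A rate that depends on how long patients happened to stay is hard to carry into a setting with different stays.

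**Working it through.** **The plan's own figure.** The only computed figure is the 95% interval for 18/20 successes. The exact (Clopper-Pearson) method gives 68.30% to 98.77%, which matches the stated 68.3% to 98.8%. The plan gives no figure for adverse events, so every rate below is an assumption.

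**Channel 1: drug events that begin after a responder leaves.** Let *f* be the risk of a drug event over a common window, *e* the share of those events that begin before responders leave, and *s* the success proportion. Assume failures are observed for the whole window. Then

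pooled rate = s·f·e + (1 − s)·f = f·[1 − s(1 − e)],

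and the fall from s = 0.5 to s = 0.9 is 0.4·f·(1 − e). With 18 responders, the expected number of patients whose event is missed is 18·f·(1 − e). Taking f = 30%:

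| Event timing (assumed) | e | Pooled, s = 50% | Pooled, s = 90% | Fall, points | Missed among 18 |
|---|---|---|---|---|---|
| All early | 100% | 30.0% | 30.0% | 0 | 0 |
| Mostly early | 90% | 28.5% | 27.3% | 1.2 | 0.5 |
| Less early | 70% | 25.5% | 21.9% | 3.6 | 1.6 |
| Constant rate over 2 h, responders leave at 1 h | 54% | 23.2% | 17.7% | 5.5 | 2.5 |
| Constant rate over 2 h, responders leave at 30 min | 28% | 19.3% | 10.7% | 8.6 | 3.9 |

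In the last two rows the risk seen in responders is 1 − 0.7^(1/2) = 16.3% and 1 − 0.7^(1/4) = 8.5%. The fall is proportional to f, so f = 10% gives a third of each value. The assumed timing drives the result, and the documents do not give it.

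**Channel 2: events in the extra stay of failures.** Section 3 says "There is significant risk associated with endoscopy, including the risks of anesthesia as well as with the physical procedure itself", so this risk is not zero. Let *p* be the event risk in the window shared by all patients and *q* the risk in the extra stay. Then

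counted proportion = p + (1 − s)(1 − p)q.

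For p from 10% to 30% and q from 10% to 50%, moving from s = 0.5 to s = 0.9 lowers it by 0.4(1 − p)q. That is 0.4 × 0.7 × 0.1 = 2.8 points up to 0.4 × 0.9 × 0.5 = 18.0 points. At the projected 18/20 only two patients have the extra stay. The addition is then 0.1(1 − p)q, or 0.7 to 4.5 points, and can never exceed 2/20 = 10 points.

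**Would an equal window be enough?** No. A window long enough to include rescue still takes in rescue events. With p = q = 30%, the rate is 0.30 + 0.5 × 0.7 × 0.3 = 40.5% at s = 0.5 and 0.30 + 0.1 × 0.7 × 0.3 = 32.1% at s = 0.9. Events after rescue need a line of their own.

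**One event found only at the call.** The table would show 0/20, with upper limit 1 − 0.025^(1/20) = 16.8%, instead of 1/20 = 5% (exact 95% interval 0.1% to 24.9%).

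**The case against.** The strongest reply is that early drug effects are already collected from everyone. Section 4.c.v takes data after each administration, including blood pressure and symptoms, and 4.c.iv adds an interview after treatment. Section 6.a describes a very short half-life. Unequal stay can hide only drug events that begin after discharge, and these may be few. This stands as a limit on size. It does not settle the matter, because 6.a also expects absorption to be slower than by the sublingual route and calls this theoretical, and Section 3 found no published use of this treatment. The timing of events is unknown.

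Second, passing the swallow test is required before discharge; the protocol does not say that patients leave at that moment. This stands, so the stay can only be said to tend to be shorter in responders.

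Third, Aim 2 speaks of events from the intervention. If only drug-attributed events were counted, channel 2 would drop out. But no attribution rule is given, and the endpoint as written covers every adverse event in the stay.

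Fourth, an event found at the call is not lost, since 4.f uses the call to look for delayed complications. This stands: the issue is that such events are left out of the frequency. The data collection form cited in 4.c.iv is not in the documents and may record event times, but that would not change what 4.f reports.

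A reader might go further and infer that a more effective drug would look safer merely because patients go home sooner. The documents do not support that. They give no discharge times or event timing, the effect is nil if all drug events are early, and there is no comparator against which the drug could look safer.

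**Conclusion.** The point holds in a limited form. The window depends in part on treatment outcome, the frequency is pooled over it, and delayed complications found at the call are not counted. The reported frequency therefore depends partly on the success rate and can miss events that begin after a responder is discharged.

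The size cannot be determined from the documents. For drug events at an assumed 30% risk, the fall between 50% and 90% success runs from 0 to 8.6 points over the timings shown, and is 1.2 points if 90% of events are early. At the projected 90% success, the extra stay of failures adds at most 10 points.

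What is affected is the interpretation of one descriptive proportion in a single-arm pilot of 20 patients. No test or between-arm comparison is at stake, and Section 4.h already says that further research is needed to assess safety. The change is worth making because it is cheap.

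**What to change.** In 4.e.ii and 4.f:

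1. Report the named Aim 2 events over one stated window of equal length from the first dose. The call comes at least 4 days after discharge, so any window of up to 4 days will have closed by then.
2. Take events from the visit record plus one added question on the existing call about the named events within that window. Count call-reported events in the frequency, mark their source, and delete the word non-statistically.
3. Show events that begin after endoscopy or other rescue treatment on a separate line.
4. Split the table by whether nitroglycerin succeeded, with the median time from last dose to discharge in each group. Length of stay, procedures, medications and dose times are already collected; confirm that discharge time is too. Add a note that 4.d counts intolerable side effects as failure, so part of any difference between the groups arises by definition.

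The cost is SAP wording, one question on a planned call and one fuller table. No treatment or discharge rule changes. The downside is that post-discharge events rest on patient recall, more so in responders, and the reported rate may be higher. A call cannot recover a blood pressure reading, so hypotension remains largely an in-hospital finding.
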